### 11.6.2. Study Population

Demography
Age

 
• Age will be calculated based on the Screening visit date
 
• Birth date will be imputed as follows:             
 
Any subject with a missing day will have this imputed as day ‘15’.
 
Any subject with a missing date and month will have this imputed as ‘30JUN’.
 
 
 

Body Mass Index

 
• Calculated as weight (kg) / [height (m)]
 

Extent of Exposure

 
• Number of days of exposure to study drug will be calculated based on the formula:             
 
Duration of Exposure in Days = Treatment Stop Date – (Treatment Start Date) + 1
 
 
 
• Participants who were randomized but did not report a treatment start date will be categorised as having zero days of exposure.
 
• The cumulative dose will be based on the formula:             
 
Cumulative Dose = Sum of (Number of Days x Total Daily Dose)
 
 
 
• If there are any treatment breaks during the study, exposure data will be adjusted accordingly.
 
• Note: GSK2879552 exposure data will only be used for the above calculation.
 

## 11.7. Appendix 7: Reporting Standards for Missing Data

### 11.7.1. Premature Withdrawals

Element	Reporting Detail
General	
 
• A subject will be considered to have completed the study if they complete screening assessments, at least 28 days of study treatment(s) and the post-treatment follow-up visit.
 
• If subjects which prematurely discontinue, additional subjects may be enrolled as replacement subjects at the discretion of the Sponsor in consultation with the investigator.
 
• Subjects who fail to take at least 75% of their scheduled doses in the first 28 days for reasons other than toxicity (e.g., dose limiting toxicities) will be replaced
 
• All available data from participants who were withdrawn from the study will be listed and all available planned data will be included in summary tables and figures, unless otherwise specified.
 
• Withdrawal visits will be summarised as withdrawal visits.
 

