6.2. Subject Completion Criteria

In Part 1, a subject will be considered to have completed the study if:

- they complete screening assessments, the 28-day DLT observation period, and taking a minimum of 75% of planned doses,
- they progress or die while receiving study treatment, or
- they are receiving ongoing study treatment at the time of the Sponsor's decision to close the study.

In Part 2, a subject will be considered to have completed the study if:

- they die while receiving study treatment,
- they progress while receiving study treatment and are followed until death, or
- they are receiving ongoing study treatment at the time of the Sponsor's decision to close the study.

Subjects who have not died, and are no longer being followed for survival are considered to have discontinued the study. The End of Study eCRF should only be completed when a subject is no longer being followed.

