7. STUDY ASSESSMENTS AND PROCEDURES

A signed, written informed consent form must be obtained from the subject prior to any study-specific procedures or assessments being performed.

The timing of each assessment is listed in the Time and Events Table (Section 7.1). The timing and number of the planned study assessments may be altered during the course of the study based on newly available data (e.g. to obtain data closer to the time of peak plasma concentrations) to ensure appropriate monitoring for the following assessments: safety, PK, PD/biomarker assessments. The change in timing or addition of time points for any of the planned study assessments listed above must be approved and documented by GSK, but this will not constitute a protocol amendment. The institutional review board (IRB) or ethics committee (EC) will be informed of any safety issues that require alteration of the safety monitoring scheme.

Whenever vital signs, 12-lead ECGs and blood draws are scheduled for the same nominal time, the assessments should occur in the following order: 12-lead ECGs, vital signs, blood draws.

If the blood draw is done first, there should be at least 15 minute interval before the vital signs and 12-lead ECGs measurements are taken.

On clinic days, study drug should be taken in the clinic after all the safety procedures (including CBC) and blood sampling for PK/PD, if applicable, are completed.

Detailed procedures for obtaining each assessment are provided in the Study Procedures Manual (SPM).

Visit Window

Informed consent should be signed within 35 days prior to dosing.

Baseline disease assessment should be completed within **21 days** prior to dosing start.

ECHO/MUGA should be completed within **35 days** prior to dosing start.

Pregnancy testing should be completed **7 days** prior to dosing start and all other screening assessments should be completed within **14 days** prior to dosing start.

Visits in the first 4 weeks will be allowed ± 1 day window. Bone marrow on Day 15 can be done between Day 8 and Day 21.

Visits beyond the first 4 weeks will have ± 3 days window.

The End of Treatment visit should be completed within **14 days** from the last dose.

Time Window for PK sampling

0.25, 0.5, 1 and 1.5 hours post dose sampling: ± 5 minutes

2, 3, 4 hours post dose sampling: ± 10 minutes

6, 8, and 10 hours post dose sampling: ± 30 minutes

24 hours post dose sampling: ± 1 hour and should be done before the next dose administration.

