20. Baseline disease assessment should be completed within 21 days prior to dosing start. Cytogenetics testing should be performed as part of disease assessment at baseline. Cytomorphology is the preferred method to determine bone marrow blast counts. However, if a bone marrow aspirate cannot be obtained for cytomorphology review, a bone marrow biopsy is strongly recommended to determine the bone marrow blast count.
21. In PK/PD expansion cohorts, PD and/or exploratory sample (peripheral blood and BMA) collection may be stopped earlier at the sponsor's discretion.
22. ATRA combination arm only.
23. Free T3 to be tested only when clinically indicated
24. At any time point in the study, if a bone marrow aspirate is found to be hemodilute (no spicules) or uninterpretable, then a bone marrow biopsy is strongly recommended to be collected at the next disease assessment time point in addition to the aspirate to ensure the conduct of a disease assessment.
25. BM slides may be evaluated for changes in morphology.
26. The Survival FU visit should be completed every 12 weeks after documented disease progression (or after initiation of another anticancer treatment). Subjects should be contacted every 12 weeks (\pm 2 weeks) until death occurs.

Table 4 Time and Events Table: Part 2 – Expansion Cohort

	SCR	First Treatment Phase (28 days)								Continuation Phase	EOT	SFU Q12W
		D 1	D4	D 8	D11	D 15	D18	D22	D25			
Office Visit	X	X	X	X	X	X	X	X	X	every 4 wks	X	
Informed consent	X											
Demography	X											
Medical history	X											
Disease characteristics	X											
Study Drug Dosing ⁹		< ----- Daily or per dosing schedule ----- >										
Review subject dosing diary				X		X				every 4 wks	X	
Study Drug Dispensing		X								every 4 wks		
Complete physical exam	X										X	
Brief physical exam		X ⁷		X						every 4 wks		
Montreal Cognitive Assessment	X	X		X		X		X		Wk 4 and every 4 wks		
ECOG PS	X	X ⁷		X						every 4 wks	X	
Vital Signs	X	X ⁷		X		X				every 4 wks	X	
Height and weight ⁶	X	X ⁷		X						every 4 wks	X	
ECHO/MUGA	X											
12-lead ECGs	X	X ⁷		X						every 4 wks	X	
HIV, HBsAg and HCV Ab testing	X											
CBC	X	X ⁷	X	X	X	X	X	X	X	Weekly x 4 wks (Wk 4-7), Wk 8 and every 4 wks ¹²	X	
Chemistry Panel including LFT	X		X ¹⁸	X	X ¹⁸	X		X		every 4 wks	X	
Fasting Lipid panel (triglyceride, cholesterol) ¹⁸	X			X		X		X		Every 4 wks		
Coagulation Panel including PT, PTT, INR, fibrinogen	X			X		x		X		every 4 wks	X	

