## 11.10.4. Study Population Tables

Study Population Tables					
No.	Population	IDSL / Example Shell	Title	Programming Notes	Deliverable
Subject Disposition					
1.1.	All Treated Subjects	ES1	Summary of Participant Disposition for the Participant Conclusion Record	ICH E3, FDAAA, EudraCT	SAC
1.2.	All Treated Subjects	SD1	Summary of Treatment Status and Reasons for Discontinuation of Study Treatment		SAC
1.3.	Enrolled	NS1	Summary of Number of Participant by Country and Site ID	EudraCT/Clinical Operations	SAC
Demographic and Baseline Characteristics					
1.4.	All Treated Subjects	DM1	Summary of Demographic Characteristics	ICH E3, FDAAA, EudraCT	SAC
1.5.	Enrolled	DM11	Summary of Age Ranges	EudraCT	SAC
1.6.	All Treated Subjects	DM5	Summary of Race and Racial Combinations	ICH E3, FDA, FDAAA, EudraCT	SAC
Medical History and Concomitant Medications					
1.7.	All Treated Subjects	MH1	Summary of Current/Past Medical Conditions		SAC
1.8.	All Treated Subjects	CM8	Summary of Concomitant Medications	Include both prior and concomitant medications	SAC
Exposure and Treatment Compliance					
1.9.	All Treated Subjects	POP_T1	Summary of Exposure to GSK2879552	Include 2mg QD/ATRA 45mg/m2/day	SAC

Study Population Tables					
No.	Population	IDSL / Example Shell	Title	Programming Notes	Deliverable
1.10.	All Treated Subjects	ODMOD1	Summary of Dose Reductions to GSK2879552		SAC
1.11.	All Treated Subjects	ODMOD8	Summary of Dose Escalations to GSK2879552		SAC
1.12.	All Treated Subjects	ODMOD2	Summary of Dose Interruptions to GSK2879552		SAC
Prior Anti-Cancer Therapy and Surgical Procedures					
1.13.	All Treated Subjects	AC1	Summary of Prior Anti-Cancer Therapy		SAC
1.14.	All Treated Subjects	AC3	Summary of Number of Prior Anti-Cancer Therapy Regimens		SAC
1.15.	All Treated Subjects	OSP1	Summary of Cancer Related Surgical Procedures		SAC

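### SAP 11.7.1 defines study completion by a single route that conflicts with the three Part 1 routes in Protocol 6.2, and SAP Table 1 does not declare the change

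*SAP*

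**What the plan says.** Protocol 6.2 lists three alternatives for Part 1, any one of which is enough:

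- Route 1: "they complete screening assessments, the 28-day DLT observation period, and taking a minimum of 75% of planned doses".
- Route 2: "they progress or die while receiving study treatment, or" the next item.
- Route 3: "they are receiving ongoing study treatment at the time of the" sponsor's decision to close the study.

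The section closes with a further rule: "Subjects who have not died, and are no longer being followed for survival are considered to have discontinued the study".

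SAP 11.7.1 gives one route. A subject has completed "if they complete screening assessments, at least 28 days of study treatment(s) and the post-treatment follow-up visit". All three conditions must be met. The 75% dosing threshold appears in the same SAP section, but only as a rule for replacing subjects.

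SAP Table 1, which sets out departures from the protocol's analysis, has three entries: no Part 2 analysis, an abbreviated report, and no ATRA pharmacokinetic analysis. Completion is not among them.

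Disposition is reported in SAP Table 1.1, "Summary of Participant Disposition for the Participant Conclusion Record", which is marked for ICH E3, FDAAA and EudraCT, and in Listing 2 (reasons for study withdrawal).

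**The concern.** The two documents give different answers to a basic question: who finished the study? The SAP rule has no place for progression, death or sponsor closure as completion. The first two are common ends to treatment in relapsed or refractory AML, and the third is pertinent because the study was terminated early. The SAP also makes completion depend on a visit it does not identify, so two programmers working from 11.7.1 could produce different completer counts.

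The stake is the disposition table and withdrawal listing, which feed the study report and public registries. If 11.7.1 drives them, subjects who completed under the protocol are shown as not completing. If the site's conclusion record drives them, the SAP text contradicts the table it accompanies.

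**Working it through.** There is no sample size, power or error rate to reproduce. The check applies both rules to the same subject histories.

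**Rules**

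- Protocol 6.2 (Part 1): completed = (screening AND 28-day DLT window AND at least 75% of planned doses) OR progression or death on treatment OR on treatment at closure. With daily dosing, 75% of 28 is 0.75 × 28 = 21 doses.
- SAP 11.7.1: completed = screening AND at least 28 days of treatment AND the follow-up visit.

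**Which visit?** The Part 1 schedule (Protocol 7.1, Table 3) has no column with the SAP's name for it. Two contacts could be meant. One is the End of Treatment visit: "The End of Treatment visit should be completed within" 14 days of the last dose. The other is the 12-weekly survival contact, a telephone call in the table but a visit in footnote 26: "The Survival FU visit should be completed every 12 weeks after documented disease progression (or after initiation of another anticancer treatment"). Protocol 6.3 and 10.3 also refer to follow-up after treatment. So the term is undefined, but contact after treatment is scheduled. Below, "visit counted" means that one of these contacts took place and is accepted.

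**Histories** (C = completed, N = not completed; Protocol 6.2's closing sentence set aside)

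| History | Protocol | SAP |
|---|---|---|
| Progresses and stops Day 20, visit counted or not | C | N |
| Progresses Day 60, visit counted | C | C |
| Progresses Day 60, no visit | C | N |
| Dies on treatment, Day 20 or Day 60 | C | N |
| On drug at closure, Day 15 | C | N |
| On drug at closure, Day 60, no later visit | C | N |
| On drug at closure, Day 60, later visit counted | C | C |
| Stops for an adverse event Day 60, visit counted | C | C |
| Withdraws consent Day 40, no visit | C | N |
| Stops drug Day 22 (22/28 = 79% of doses), DLT window observed, visit counted | C | N |
| 28 days of treatment, 60% of doses, stops for another reason, visit counted | N | C |

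**Reading the table**

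1. Death on treatment always changes status, because no visit after treatment is possible.
2. Progression that ends treatment before 28 days always changes status, because the treatment condition fails. (Protocol 6.3 allows treatment past progression by agreement; such a subject could still reach 28 days.)
3. With at least 28 days of treatment, progressors and subjects on drug at closure change only if no visit is counted.
4. The last row moves the opposite way, because the SAP drops the 75% condition. It takes 28 days as elapsed time from first to last dose.

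**Protocol 6.2's own loose end.** Its closing sentence calls a living subject who is no longer followed for survival discontinued. The sentence does not say whether it covers Part 1. If it does, a subject can meet Route 1 and still be discontinued.

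**The case against.** The strongest reply is that nothing may be reclassified. Table 1.1 is titled as a summary of the conclusion record, SAP 6.2 presents withdrawal reasons in eCRF order, and the derived-data appendix (SAP 11.6) contains no algorithm for completion. The SAP definition is one bullet in a missing-data appendix. If status is taken from a record that sites completed under Protocol 6.2, the table is right and only the text is wrong. This stands as far as it goes: the SAP does not state the source, so harm to the table is conditional. It does not rescue the text, which would then describe a rule the table does not follow.

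A second reply is that the consequence is narrow. Study population, safety and efficacy displays mainly use All Treated Subjects, PK uses the PK population, and SAP 11.7.1 keeps available planned data from withdrawn subjects. That stands in full.

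Three stronger readings are tempting, and the documents do not support them.

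- A reader might infer that the visit does not exist, so that almost nobody can complete. That follows only if the End of Treatment visit and the survival contact are both refused.
- A reader might infer that all progressors and everyone on drug at closure change status. The Day 60 rows with a counted visit show otherwise.
- A reader might size the problem from Protocol 1.3.4, where 11 AML subjects had single-dose and 8 had repeat-dose PK data by 20-NOV-2015 (11 − 8 = 3; 3/11 = 27%). Those are PK counts at an interim cut. A missing repeat-dose profile may mean that Day 15 was not yet reached, or a missed sample, and it does not identify progression or death. Dose-group sizes from that date have the same limit, since the SAP adds later groups without giving their sizes.

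**Conclusion.** The conflict is real. SAP 11.7.1 states a completion rule that differs from Protocol 6.2, rests on an undefined visit and is not declared in SAP Table 1. This is a wrong stated rule, not just missing detail.

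If the rule is applied, deaths on treatment and progressions that end treatment before 28 days always move from completed to not completed. So does any subject on drug at closure with under 28 days of treatment or no counted later visit. A subject with 28 days of treatment but under 75% of doses who stops for another reason can move the other way. The number of subjects affected cannot be computed from the documents.

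Whether reported attrition is actually distorted depends on an unstated fact: whether disposition is derived from 11.7.1 or read from the conclusion record. That sites completed that record under Protocol 6.2 is an assumption. On either branch the effect stops at Table 1.1 and Listing 2. It should be corrected, but it has no bearing on the safety, response or PK conclusions.

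**What to change.** 1. Replace the first bullet of SAP 11.7.1 with the three Part 1 completion routes of Protocol 6.2.
2. Remove the follow-up visit condition.
3. State that Table 1.1 and Listing 2 take status from the conclusion record completed under Protocol 6.2, after confirming that sites completed it on that basis.
4. Reconcile this with the closing sentence of Protocol 6.2: say whether it applies to Part 1 and, if so, how a living subject who met Route 1 but is no longer followed for survival is reported.

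The cost is wording. No new data are needed if the conclusion record follows Protocol 6.2. If the check in step 3 shows that it does not, status would have to be derived from dosing, progression, death and closure data.

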### 11.7.2. Handling of Missing Data

Element	Reporting Detail
General	
 
• Missing data occurs when any requested data is not provided, leading to blank fields on the collection instrument:                             
 
○ These data will be indicated by the use of a “blank” in subject listing displays. Unless all data for a specific visit are missing in which case the data is excluded from the table.
 
○ Answers such as “Not applicable” and “Not evaluable” are not considered to be missing data and should be displayed as such.
 
 
 

Outliers	
 
• Any participants excluded from the summaries and/or statistical analyses will be documented along with the reason for exclusion in the clinical study report.
 

#### 11.7.2.1. Handling of Missing and Partial Dates

Imputed partial dates will not be used to derive study day, duration (e.g. duration of adverse events), or elapsed time variables.

Imputed dates will not be displayed in listings. However, where necessary, display macros may impute dates as temporary variables for the purpose of sorting data in listings only. In addition, partial dates may be imputed for ‘slotting’ data to study time periods or for specific analysis purposes as outlined below.

Dataset	Date	Missing Element	Rule
Adverse Events (AE)	Start Date	day, month, and year	
 
• No Imputation for completely missing dates
 

		day,	
 
• If study treatment start date is missing (i.e. subject did
 

Dataset	Date	Missing Element	Rule
		month	
not start study treatment), then set start date = January 1.
 
 
• Else if study treatment start date is not missing:                             
 
○ If year of start date = year of study treatment start date then                                     
 
• If stop date contains a full date and stop date is earlier than study treatment start date then set start date = January 1.
 
• Else set start date = study treatment start date.
 
 
 
○ Else set start date = January 1.
 
 
 

		Day	
 
• If study treatment start date is missing (i.e. subject did not start study treatment), then set start date = 1st of month.
 
• Else if study treatment start date is not missing:                             
 
○ If month and year of start date = month and year of study treatment start date then                                     
 
• If stop date contains a full date and stop date is earlier than study treatment start date then set start date= 1st of month.
 
• Else set start date = study treatment start date.
 
 
 
○ Else set start date = 1st of month.
 
 
 

	End Date		
 
• No imputation for partial end dates will be performed
 

**Concomitant Medication and Blood and Blood Supportive Care Products:**

Start and end dates may be imputed for use in derivation of the reference variables concomitant medication start and end relative to treatment and blood and blood supportive care start and end relative to treatment, but should not be permanently stored in the analysis datasets.

Dataset	Date	Missing Element	Rule
Concomitant Medication  Blood and Blood Supportive Care Products	Start Date	day, month, and year	
 
No Imputation for completely missing dates
 

		day, month	
 
If study treatment start date is missing (i.e. subject did not start study treatment), then set start date = January 1.
 
Else if study treatment start date is not missing: 
 
If year of start date = year of study treatment start date then 
 
If stop date contains a full date and stop date is earlier than study treatment start date then set start date = January 1.
 
Else set start date = study treatment start date.
 
 
 
Else set start date = January 1.
 
 
 

		day	
 
If study treatment start date is missing (i.e. subject did not start study treatment), then set start date = 1st of month.
 
Else if study treatment start date is not missing: 
 
If month and year of start date = month and year of study treatment start date then 
 
If stop date contains a full date and stop date is earlier than study treatment start date then set start date = 1st of month.
 
Else set start date = study treatment start date.
 
 
 
Else set start date = 1st of month.
 
 
 

	End Date	day, month, and year	
 
No Imputation for completely missing dates
 

		day, month	
 
If partial end date contains year only, set end date = earliest of December 31 or date of last contact.
 

		day	
 
If partial end date contains month and year, set end date = earliest of last day of the month or date of last contact.
 

**11.7.3. Imputation of Missing Exposure End Dates**

For subjects who have missing end dates in their last exposure record potentially due to being lost to follow-up, the last contact date will be imputed as the last exposure date (i.e. date of last dose). This imputation will only be used when needed.

## **11.8. Appendix 8: Values of Potential Clinical Importance**

### **11.8.1. Laboratory Values**

Reference ranges for all laboratory parameters collected throughout the study are provided by the laboratory. A laboratory value that is outside the reference range is considered either high abnormal (value above the upper limit of the reference range) or low abnormal (value below the lower limit of the reference range). Note: a high abnormal or low abnormal laboratory value is not necessarily of clinical concern. The laboratory reference ranges will be provided on the listings of laboratory data.

To identify laboratory values of potential clinical importance, National Cancer Institute Common Terminology Criteria for Adverse Events (NCI-CTCAE v4.0) will be used to assign grades to the relevant laboratory parameters.

